6.4. Multiple Comparisons/Multiplicity

There is no plan to formally adjust for multiplicity.

6.5. Use of an “Efficacy Subset” of Participants

There are no plans to use a modified efficacy subset.

6.6. Participant Disposition

The summary of participant disposition has been described in the H0P-MC-CPMP SAP Version 5. Kaplan Meier plot of time to last dosing by treatment group will also be provided to describe patient disposition.

6.7. Participant Characteristics

The summary of participant characteristics has been described in the H0P-MC-CPMP SAP Version 5.

ISA-specific considerations are described below.

- painDETECT ≥ 19 (ie, Positive for neuropathic pain)
- Roland Morris Disability Questionnaire (RMDQ) Total Score at baseline.

6.8. Treatment Compliance

Treatment percentage of compliance will be calculated as:

$$\frac{\text{Total pills taken} * 100}{\text{Total pills expected}}$$

with total pills taken calculated by total pills dispensed – total pills returned. A patient is considered to be compliant overall if the percentage is between 80% and 120% from Visit 4 to 7. The percentage of patients who are compliant with the study drug will be summarized by treatment group.

6.9. Concomitant Therapy

The summary and reporting of concomitant therapy have been described in the H0P-MC-CPMP SAP Version 5. As described in Section 6.2, PainDETECT will additionally be included as a covariate for modelling rescue medication.

6.10. Efficacy Analyses

6.10.1. Primary Outcome and Methodology

The analysis of the primary outcome has been described in the H0P-MC-CPMP SAP Version 5. The longitudinal model will include average NRS during the preliminary data entry period (PDEP, last 7 days prior to randomization at Visit 3) and within each nominal week of the double treatment period as a longitudinal outcome. As noted in Section 4.1, the endpoint for the primary analysis is defined as 8 weeks post initial treatment administration.

6.10.2. Additional Analyses of the Primary Outcome

The overall mean treatment effect in change from baseline over the double blind treatment period will be reported for evaluating treatment effect for NRS, VAS, Roland Morris Disability Questionnaire (RMDQ), as well as other secondary continuous efficacy endpoints.

6.10.3. Secondary Efficacy Analyses

The RMDQ is a simple, sensitive, and reliable method to measure disability in patients with back pain. The RMDQ consists of 24 statements relating to the person's perceptions of back pain and associated disability based on

- physical ability/activity
- sleep/rest
- psychosocial
- household management
- eating, and
- pain frequency.

Participants are asked if they feel the statement is descriptive of their circumstances on that day. The total score is obtained by counting the number of “Yes” responses, ranging from:

0 = no disability to 24 = maximal disability.

A Bayesian longitudinal mixed-effect model repeated measures (MMRM) analysis will be performed to evaluate the change from baseline to each postbaseline visit for the RMDQ total score. The model will utilize the constrained cell means model so that a common means is estimated at the baseline. More details on this approach are provided in the H0P-MC-CPMP SAP Version 5.

This table describes the information included in the model.

Categorical effects	
 The interaction of treatment and timepoint (constrained to estimate a common mean at baseline across treatments) Average baseline pain severity category (baseline NRS <7, baseline NRS \geq7) Presence of neuropathic pain (painDETECT \geq19, painDETECT <19) Pooled investigative site
Continuous covariates	
 None

Other Secondary Analysis

The proportion of participants in each treatment group meeting prespecified binary efficacy outcomes will be calculated for each post baseline time point and will be used to compare treatment groups. The prespecified binary efficacy outcomes include the proportion of participants:

- with a reduction \geq 30%, 50%, and 70% from baseline as measured by the RMDQ score, and
- with at least a 3.5 point reduction from baseline in the RMDQ score.

A Bayesian pseudo-likelihood-based categorical repeated measures regression model that includes all post baseline observations will be used to estimate the probability of achieving the response level in each treatment group and will be used to compare treatment groups.

The model will include the categorical and continuous covariates described for the key secondary analysis. In addition, the time to first treatment response from baseline based on the prespecified binary thresholds above will be assessed. Analyses will be conducted according to the time to event analyses specified in the CPMP SAP Version 5.

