4.1. Primary Objective

The primary objective of this Intervention-Specific Appendix (ISA) is stated in the H0P-MC-CPMP. For H0P-MC-BP03, an endpoint is defined as 8 weeks post initial treatment administration at Visit 7. The timepoint for secondary endpoint measurements is the same as the primary endpoint except for the overall measures.

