4.2. Secondary Objectives

Secondary objectives applicable to all ISAs are listed in the H0P-MC-CPMP SAP Version 5.

Additional secondary endpoints specific to H0P-MC-BP03 are listed below.

Objective	Endpoint Measure
Other Secondary	
Physical Functioning Efficacy of LY3556050 versus placebo	
Change from baseline to endpoint for the Roland-Morris Disability Questionnaire (RMDQ) total scoreProportion of participants with a reduction from baseline of at least 3.5 points on RMDQ total scoreProportion of participants with a reduction from baseline $\geq 30\%$, 50%, and 70% on the RMDQ total scoreTime to first treatment response with at least 30%, 50%, and 70% reduction from baseline in RMDQ total scoreOverall mean change from baseline to endpoint for the RMDQ total score
Efficacy of LY3556050 versus placebo	
Overall mean change from baseline assessment for average pain intensity numerical rating scale (NRS) during the treatment phase

CCI

5. Study Design

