6.2. Adjustments for Covariates

The general adjustment strategy has been described in the H0P-MC-CPMP SAP Version 5.

Randomization into H0P-MC-BP03 is stratified by the presence of neuropathic pain as defined by the painDETECT score (Freynhagen et al. 2006).

The following stratification factor will be included in the models for the primary, secondary, and some exploratory outcomes.

Neuropathic pain	painDETECT score
Positive presence	≥19
Unclear or negative	<19

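### The RMDQ responder models take their covariates from an unlabelled key secondary analysis; on the nearest reading, baseline RMDQ is left out

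*SAP*

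**What the plan says.** SAP Section 4.2 lists the RMDQ endpoints, including the 3.5-point, 30%, 50% and 70% responder proportions, as other secondary endpoints specific to BP03. Section 4.1 sets their time point: "The timepoint for secondary endpoint measurements is the same as the primary endpoint except for the overall measures". That is week 8.

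Section 6.10.3 first describes a Bayesian MMRM for the RMDQ total score and tabulates its terms: treatment by timepoint ("constrained to estimate a common mean at baseline across treatments"), baseline NRS category, painDETECT category and pooled site. The row for continuous covariates reads None.

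For the responder endpoints it then plans "A Bayesian pseudo-likelihood-based categorical repeated measures regression model that includes all post baseline observations", to "estimate the probability of achieving the response level in each treatment group". Their covariates are set by one sentence: "The model will include the categorical and continuous covariates described for the key secondary analysis".

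Two sections defer to a document that was not supplied. Section 4.2 says "Secondary objectives applicable to all ISAs are listed in the H0P-MC-CPMP SAP Version 5", and Section 6.2 says "The general adjustment strategy has been described in the H0P-MC-CPMP SAP Version 5". Section 6.7 lists "Roland Morris Disability Questionnaire (RMDQ) Total Score at baseline" among the participant characteristics, so the score will be available.

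**The concern.** The covariate sentence has no labelled target in either document. On the nearest reading, it carries a list built for one model into another where that list no longer works.

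In the total-score MMRM, baseline RMDQ is one of the modelled outcomes and the arms share a baseline mean, so no baseline covariate is needed. The responder model has no baseline record. The constraint has nothing to act on, and baseline RMDQ does not enter at all.

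Response is nevertheless defined from baseline. RMDQ is a whole-number count from 0 to 24, so a reduction of at least 3.5 points means at least 4 points, which a participant starting at 3 or below cannot achieve. Baseline NRS category measures pain, not disability, and is only a partial proxy.

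At stake are some precision and, depending on who drops out, possibly the balance of the comparison. A programmer also cannot tell from this SAP which model to fit.

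**Working it through.** The documents give no power or precision figure for the RMDQ responder analyses, so there is none to reproduce. The efficacy criterion, the allocation and the assumptions behind the trial-level false-positive rate (below 0.1) are redacted, so that figure cannot be rebuilt either. It does not concern these endpoints.

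**1. Inputs from the documents.** SAP Section 5.2 gives up to 200 randomised and about 33% dropout: 200 × (1 − 0.33) = 134 completers. Every other input below is an assumption.

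**2. Measure.** The risk difference is the mean over participants of p(LY, x) − p(placebo, x), where x is the covariate vector. The variance ratio is VR = Var(risk difference without baseline RMDQ) / Var(with it).

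**3. Repeated-measures simulation** (3000 trials in each of 12 scenarios). Assumed:
- 200 randomised, 1:1 or 2:1
- baseline RMDQ mean 10 or 12, SD 5
- slope of follow-up on baseline 0.4, 0.6 or 0.8; residual SD 4.5; within-person correlation 0.6
- week-8 placebo improvement 2.5 points and LY benefit 2 points
- RMDQ collected at weeks 2, 4, 6 and 8
- 33% monotone dropout by week 8, completely at random
- latent correlation of 0.3 between NRS category and RMDQ; 30% painDETECT-positive; 8 pooled sites

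The model was a logistic GEE with the Section 6.10.3 terms, with and without continuous baseline RMDQ. Ranges are over allocation and baseline mean; the Monte Carlo SE of VR is at most 0.020.

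| Threshold | Baseline-to-week-8 correlation 0.39 | 0.53–0.54 | 0.64–0.65 |
|---|---|---|---|
| 3.5 points | 1.19–1.23 | 1.09–1.17 | 1.03–1.08 |
| 30% | 1.04–1.05 | 1.00–1.01 | 1.00–1.01 |
| 50% | 1.00 | 1.00–1.01 | 1.04–1.05 |
| 70% | 1.00–1.01 | 1.01–1.04 | 1.07–1.11 |

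At a nominal one-sided 10% level, adding the term changed power by 1 to 7 points for the 3.5-point endpoint and by −1 to 4 points for the percentage thresholds. Type I error was 0.083–0.105 without the covariate and 0.081–0.106 with it.

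**4. Single-visit logistic simulation** (134 completers; 600 replicates in each of 48 scenarios). Assumed: baseline mean 11 or 14, SD 5; correlation 0.3, 0.5 or 0.7; placebo drop 3.5 points; treatment effect 2.5 points; 1:1 or 2:1; adjustment for NRS category. For example, with 1:1 allocation, mean 11, correlation 0.3 and the 3.5-point endpoint, the empirical SDs were 0.0836 without and 0.0734 with the covariate, so VR = (0.0836 / 0.0734)² ≈ 1.30. Over all scenarios VR was 1.02–1.30 for 3.5 points, 0.99–1.08 for 30%, 0.97–1.09 for 50% and 0.99–1.13 for 70%. Monte Carlo error is a few percent. At a two-sided 5% level, the power lost by omission was about 3 to 10 points for 3.5 points, and up to about 9 points for 70%.

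**5. Wider baseline range.** Further single-visit runs at baseline means 10, 14 and 16 gave VR of about 1.01–1.31 for 3.5 points and 0.98–1.15 for the percentage thresholds.

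**6. Translation.** SE inflation is √VR − 1: √1.30 = 1.14 and √1.15 = 1.07, so at most about 14% and 7%. A VR of 1.30 is like having 134 / 1.30 ≈ 103 completers instead of 134; a VR of 1.15 is like having 134 / 1.15 ≈ 117.

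**7. Dropout not at random.** In an illustration where dropout depended on baseline RMDQ differently by arm, the 3.5-point risk difference was about 0.155 with baseline RMDQ in the model and 0.094 without it, a gap of 0.061. The mechanism was assumed, so this shows that bias is possible, not how large it would be in this trial.

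**The case against.** The strongest reply is that the pointer is a slip of label. The table in Section 6.10.3 is the only covariate list there, and its two rows, categorical and continuous, match the wording of the sentence. When that section relies on the CPMP SAP it says so, for the constrained model and for time to response; this sentence cites nothing. That is a fair reading, but it leads directly to a responder model without baseline RMDQ.

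The opposite reply is that Version 5 defines a key secondary analysis and may adjust for the baseline score. This cannot be excluded. In that case only the missing cross-reference remains, and the sizes above do not apply. A reader might therefore infer that the plan certainly omits baseline RMDQ; the documents do not support that.

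It is also fair to say that omitting a prognostic covariate from an other-secondary model is a choice, not an error, and that the sizes rest on assumed RMDQ distributions. In one single-visit run at baseline mean 16 and slope 0.8, the ratios were 1.01, 1.00, 1.01 and 0.99 for the 3.5-point, 30%, 50% and 70% thresholds, so there was no detectable gain. Any ranking of thresholds by gain thus depends on baseline severity as well as on the correlation, and the documents give neither.

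**Conclusion.** The point stands at low severity. The covariate pointer has no labelled target, and its nearest reading leaves baseline RMDQ out of the responder models. Omission then raises the variance of the week-8 risk difference by roughly 1% to 30% for the 3.5-point endpoint and about 0% to 15% for the percentage thresholds. These ranges assume the RMDQ distributions above, dropout completely at random, and frequentist models standing in for the Bayesian one.

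Two stronger readings go too far in opposite directions. One is that the planned comparison is biased. Randomisation protects it at entry, and nothing in the documents shows that dropout depends on baseline RMDQ differently by arm. The other is that only precision is at risk. With about 33% dropout that holds only if such dependence is absent. The multiple-imputation sensitivity analysis specified in SAP Section 6.3 covers VAS and NRS, not the RMDQ responders.

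Severity is low because these are other-secondary endpoints with no stated power or decision rule, and no multiplicity adjustment is planned.

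**What to change.** In SAP Section 6.10.3, replace the pointer with an explicit list for all four thresholds: treatment, post-baseline timepoint and their interaction, baseline NRS category, painDETECT category, pooled investigative site, and baseline RMDQ total score as a continuous covariate. State that the response probabilities already planned for each arm are averaged over the observed covariates, and report their difference. An adjusted odds ratio is conditional, so its meaning changes with the covariate set. If a Version 5 analysis was meant, cite its section and add baseline RMDQ if it is absent.

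The cost is one or two sentences and one model parameter, with at most about 1% to 2% loss of precision for some percentage thresholds under dropout at random. No participants, visits or procedures are added. The added term does not protect against dropout that depends on unobserved outcomes.

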6.11. Bioanalytical and Pharmacokinetic/Pharmacodynamic Methods

The observed plasma concentrations for LY3556050 will be reported graphically and summarized descriptively. Exploratory model-based pharmacokinetic (PK) and PK-pharmacodynamic (PD) analyses may be conducted to characterize the PK of LY3556050 in participants with chronic low back pain and to assess exposure-response relationships for efficacy and safety outcomes. Participant factors may be investigated to assess their effects on model parameters. Additional analyses may be conducted, as needed. Data from this study may be pooled with data from other studies, if appropriate.

6.12. Safety Analyses

The general analysis of safety has been described in the H0P-MC-CPMP SAP Version 5. However, additional ISA-specific safety considerations are described in the sections below.

6.12.1. Extent of Exposure

Duration of exposure (defined as the time since the first dose of study treatment to the last dose of study treatment in days) to study drug will be summarized by treatment group using descriptive statistics; the summary will also include the total exposure in patient years.

Duration of exposure (days):

= Date of the last dose during the double blind treatment period – Date of the first dose for the treatment period +1

Total exposure in patient years will be calculated as follows:

Total exposure in patient years = Sum of duration (days) of exposures for all patients in the treatment group/365.25

See Section [6.16](#) for additional dosing analyses.

6.12.2. Deaths, Other Serious Adverse Events, and Other Adverse Events for Review

Treatment-emergent adverse events by preferred term will be reported.

In addition to an overall listing, additional lists by terms or organ systems of interest, including cardiovascular, thyroid, and renal functions, will be generated.

The full summary of adverse events is described in the H0P-MC-CPMP SAP. Other adverse events for review coded to Medical Dictionary for Regulatory Activities (MedDRA) terms include

- Hypothyroidism (in SMQ)
- Cardiac arrhythmias (in SMQ)
 - Arrhythmia related investigations, signs, and symptoms
 - Bradyarrhythmia terms, nonspecific
 - Cardiac arrhythmia terms, nonspecific
 - Conduction defects
 - Disorders of sinus node function
 - Supraventricular tachyarrhythmias
 - Tachyarrhythmia terms, nonspecific
 - Ventricular tachyarrhythmias
- Hypotension (in preferred MedDRA term)
 - Orthostatic hypotension
 - Blood pressure ambulatory decreased
 - Blood pressure decreased
 - Blood pressure diastolic decreased
 - Blood pressure systolic decreased
 - Blood pressure orthostatic decreased
 - Dizziness

- Dizziness exertional
- Presyncope
- Syncope
- Abnormal renal function (in MedDRA HLT)
 - Renal function analyses
 - Renal failure and impairment
- MACE (including MI and stroke)
 - Death (preferred MedDRA term)
 - Cardiac arrest (preferred MedDRA term)
 - Cardiac death (preferred MedDRA term)
 - Sudden cardiac death (preferred MedDRA term)
 - Sudden death (preferred MedDRA term)
 - Ischaemic heart disease (SMQ)
 - Ischaemic central nervous system vascular conditions (SMQ)
- Depression (in MedDRA HGLT)
 - Depressed mood disorders and disturbances
- Congestive Heart Failure (in SMQ)
 - Cardiac Failure
- Substance abuse (in MedDRA HLT)
 - Substance related and addictive disorders

Narratives will be provided for patients with the following “notable” events, in addition to the “notable” events listed in the H0P-MC-CPMP SAP.

- Treatment-emergent elevated amylase or lipase $>3x$ ULN
- Renal treatment-emergent adverse events.

CCI

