#### Medical Conditions

- [2026] have a history within 2 years prior to Visit 1 or current evidence of syncope, presyncope, uncontrolled vertigo, or postural dizziness, judged to be clinically significant by the investigator
- [2027] have a QRS interval  $\geq 120$  msec at Visit 1 or Visit 2
- [2028] have a non-evaluable PR interval or a PR interval  $> 200$  msec at Visit 1 or Visit 2
- [2029] have a heart rate  $< 40$  bpm at Visit 1 or Visit 2
- [2030] have an estimated glomerular filtration rate (eGFR) of less than 60 ml/min/1.73 m^2 based on the Chronic Kidney Disease Epidemiology Collaboration (CKD-EPI) formula at Visit 1 or Visit 2
- [2031] have clinically significant active thyroid disease, including Hashimoto's thyroiditis

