6.3. Handling of Dropouts or Missing Data

The missing data strategy has been described in the H0P-MC-CPMP SAP Version 4.

In addition, to use of Bayesian MMRM model described in the H0P-MC-CPMP SAP, to examine the effect of missing data, constrained cell means MMRM with multiple imputations will be applied as a sensitivity analysis to assess change from baseline to postbaseline measure for visual analog scale (VAS) and NRS.

For these continuous efficacy endpoints, a Markov chain Monte Carlo method will be used to impute intermittent (non-monotone) missing visit data and a set of Bayesian regressions will be used for the imputation of monotone dropouts. The variable pooled investigative site, treatment, age, gender, baseline pain severity categories will be included for imputing non-monotone missingness, and primary adverse events (AEs) leading to treatment discontinuation can be included as an additional variable for imputing monotone missingness. Subject-level indicator of primary AEs leading to treatment discontinuation is set 1 for patients experiencing AEs in preferred terms (PT), including nausea, dizziness, fatigue, abdominal discomfort, abdominal pain lower, abdominal pain upper, constipation, lethargy, somnolence, at any time during double-blinded (DB) treatment period; 0 otherwise. The number of imputed data sets will be 200 and the initial seed for imputing intermittent missing data is 12345 and for imputing monotone missing

data is 678910. Within the program, the seed will be used to generate 200 seeds needed for imputation.

The analysis model will utilize the constrained cell means MMRM so that a common mean is estimated at the baseline for each imputed dataset. The pooled investigative site, treatment and time interaction, baseline pain severity categories will be included as fixed effects. Results across the imputed datasets will be aggregated using SAS procedure MIANALYZE in order to compute LSmeans and standard errors for the treatment comparisons.

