6.17. Totality of Evidence for Safety

The totality of evidence for safety analysis has been briefly described in the H0P-MC-CPMP SAP Version 5. The key safety events to be considered for H0P-MC-BP03 are listed below by domain:

General Adverse Event Information

- Serious adverse events related to study treatment
- Study discontinuation due to adverse event
- Treatment discontinuation due to adverse event
- Treatment discontinuation due to gastrointestinal disorders
- Treatment discontinuation due to potential nervous system disorder.

Cardiovascular

- QTc prolongation: >60 msec increase
- Serious cardiac disorders adverse event
- Cardiac Failure
- Arrhythmia Event
- MACE
- Hypotension event.

Liver function

- Hy's Law case: Serum total bilirubin ≥ 2 and ALT ≥ 3 for at least one visit during the double-blind treatment period.

Metabolic function

- Serious hypoglycemia adverse event
- Treatment-emergent HbA1c: Shift from low/normal at baseline to high at least once during the double-blind treatment period.

Renal function

- Treatment-emergent abnormal eGFR based on Cystatin C: Shifts
 - Mild at baseline to moderate/severe during the double-blind treatment period
 - Moderate at baseline to severe during the double-blind treatment period
- Serious renal event.

Thyroid

- Hypothyroidism.

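### The SAP's hypotension term group counts unspecified dizziness but has no postural-dizziness term, and the matching key safety event is left undefined

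*SAP*

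**What the plan says.** SAP 6.12.2 names groups of adverse events for review. One is headed "Hypotension (in preferred MedDRA term"). Under it stand orthostatic hypotension, five terms for decreased blood pressure (among them "Blood pressure orthostatic decreased"), plain dizziness, "Dizziness exertional", presyncope and syncope: ten terms in all. The list is readable throughout, with no redaction inside it. No postural-dizziness term appears.

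SAP 6.17 introduces its list with "The key safety events to be considered for H0P-MC-BP03 are listed below by domain". Its cardiovascular domain has six entries, one of which is "Hypotension event". The section neither defines that entry nor refers back to 6.12.2.

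Three other places bear on the point:

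- Protocol 5.2, criterion [2026], excludes people with a recent history or "current evidence of syncope, presyncope, uncontrolled vertigo, or postural dizziness, judged to be clinically significant by the investigator".
- Protocol 2.3.1 names orthostatic vital signs among the cardiovascular safety parameters to be evaluated.
- SAP 6.3 defines an indicator for the primary AEs leading to treatment discontinuation from nine preferred terms, "including nausea, dizziness, fatigue, abdominal discomfort" and five others. It gives no frequencies.

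**The concern.** The choice of terms fits neither of the two purposes such a group could serve. A broad screen would take in the positional form of dizziness, since it already takes in the unspecified and exertional forms. A specific haemodynamic group would leave out plain dizziness. The listed group admits the least specific complaint and omits the one most closely tied to standing up, which the protocol itself treats as a companion of syncope and presyncope.

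What is at stake is how one composite reads in the totality-of-evidence assessment. If 6.17 uses this group, postural dizziness coded to its own term would not count. Unspecified dizziness could then either blur a real difference in blood-pressure-related events or produce an apparent difference that has nothing to do with blood pressure.

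**Working it through.** **Comparison of the texts**

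| Complaint | Criterion [2026] | SAP 6.12.2 hypotension group |
|---|---|---|
| Syncope | named | listed |
| Presyncope | named | listed |
| Postural dizziness | named | not listed |
| Exertional dizziness | not named | listed |
| Unspecified dizziness | not named | listed |

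This comparison establishes the point and needs no arithmetic.

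**Illustration of size**

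The plan states no figure for this event, so there is none to reproduce. Every rate below is an assumption. The documents give only the total, up to 200 participants. The allocation ratio is redacted, so I take 100 per arm, or 133 on LY3556050 and 67 on placebo. Dropout is ignored.

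Let s be the rate of the specific terms (hypotension, blood pressure, syncope) and d the rate of plain dizziness, assumed independent.

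- Composite rate: c = 1 − (1 − s)(1 − d).
- Share of composite cases counted through dizziness alone: (c − s)/c.
- Chance of two-sided p < 0.05: Φ[(|c₁ − c₂| − 1.96·SE₀)/SE₁], with SE₀ pooled and SE₁ unpooled. With counts this small the normal approximation is rough.

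*Dilution: s = 1% on placebo and 6% on LY3556050, d equal in both arms.* Worked example for d = 5%:

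- Placebo: 1 − 0.99 × 0.95 = 0.0595.
- LY3556050: 1 − 0.94 × 0.95 = 0.1070.
- Ratio 0.1070/0.0595 = 1.80; difference 4.75 points.
- Share through dizziness alone: 0.0495/0.0595 = 83% on placebo and 0.0470/0.1070 = 44% on LY3556050.

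| d | Placebo | LY3556050 | Ratio | Difference (points) | Share through dizziness alone: placebo / LY3556050 | Chance of p < 0.05: 1:1 / 2:1 |
|---|---|---|---|---|---|---|
| 0 | 1.0% | 6.0% | 6.0 | 5.00 | 0 / 0 | 48.5% / 34.2% |
| 2% | 2.98% | 7.88% | 2.64 | 4.90 | 66% / 24% | 33.2% / 24.1% |
| 5% | 5.95% | 10.70% | 1.80 | 4.75 | 83% / 44% | 22.8% / 17.4% |
| 10% | 10.90% | 15.40% | 1.41 | 4.50 | 91% / 61% | 15.4% / 12.6% |
| 15% | 15.85% | 20.10% | 1.27 | 4.25 | 94% / 70% | 11.9% / 10.2% |

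With s = 4% against 1%, the ratio goes from 4.0 to 1.48, 1.25 and 1.16 at d = 5%, 10% and 15%. The difference goes from 3.0 points to 2.85, 2.70 and 2.55.

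*Mimicry: s = 1% in both arms, 100 per arm, dizziness raised on LY3556050 for reasons unrelated to blood pressure.* If dizziness is 5% against 15%, the composite is 5.95% against 15.85% and reaches p < 0.05 with probability 61%. If it is 2% against 5%, the probability is 17%.

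*Uncounted cases.* Postural dizziness coded separately at 1% to 5% would leave 1 to 5 participants per 100 outside the composite.

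**The case against.** The case against giving this much weight is strong in several respects.

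- **The signal is not lost from the study.** Every treatment-emergent event is reported by preferred term, the group already holds two orthostatic terms, and SAP 6.12.4 analyses measured orthostatic falls and pulse rises. This stands and confines the point to one composite. It does not repair that composite. The schedule of activities asks explicitly for supine and standing readings before and after dosing only at Visits 3, 5 and 7. Symptoms between visits reach the data as adverse events.
- **The link to 6.17 is inferred.** SAP 6.17 cites no list and defers the method to the master SAP, which was not available. SAP 6.12.2 also introduces its groups in language that need not be exhaustive and refers to the master SAP for the full summary. This stands, so the consequence is conditional.
- **A reader might infer that dizziness swamps the event.** The documents do not support that, because no dizziness or hypotension rate is given. In the first illustration dizziness supplies most LY3556050 cases at 10% and 15%, but not at 2% or 5%, and the risk difference barely moves.
- **A reader might infer that an AE coded simply as hypotension is left out.** In the heart failure, depression and substance abuse groups the heading is only a label. But the hypothyroidism heading has no sub-items and must be its own search term, and the hypotension heading mentions the preferred term. This is an ambiguity, not a demonstrated omission.
- **Coding is not shown.** Criterion [2026] governs eligibility, and the documents do not reproduce the dictionary. The omission has an effect only where a separate postural-dizziness term exists and reports are coded to it.
- **A broad review list is defensible.** That is so, but breadth does not explain leaving out the positional form.

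**Conclusion.** The point holds, at minor severity. The hypotension group in SAP 6.12.2 includes unspecified and exertional dizziness and omits a postural-dizziness term that would sit naturally beside the complaints in criterion [2026]. That much is plain text. The consequence for SAP 6.17 rests on two assumptions: that the key safety event uses this group, and that postural dizziness is coded to its own term.

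Dilution and mimicry are both possible. Their size cannot be stated from the documents, and the figures above show only how the composite behaves under assumed, independent rates. SAP 6.17 as published lists events to be considered and shows no threshold, so a changed safety decision is not demonstrated. The primary analysis and the sample size are unaffected.

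**What to change.** In SAP 6.12.2, add the postural-dizziness preferred term, where the dictionary version in use has one, or give the reason for leaving it out. List hypotension as an explicit search term so that the heading need not be interpreted. In SAP 6.17, state that the hypotension event uses the 6.12.2 list. Report the event twice, once on the full list and once without unqualified dizziness, so that a reader can see whether a difference comes from the specific terms.

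The cost is two terms, one sentence and one extra table row. The full-list count may rise slightly.

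### The MACE category in SAP 6.12.2 is labelled as including stroke, but its only CNS search is named ischaemic, so a non-fatal haemorrhagic stroke would fall outside the MACE count

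*SAP*

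**What the plan says.** SAP 6.12.2 sets out adverse-event categories for review and the MedDRA searches that define each. One category is headed "MACE (including MI and stroke"). Under it stand seven items. Five are preferred terms for death or cardiac arrest, beginning with "Death (preferred MedDRA term"). The other two are standardised MedDRA queries (SMQs): "Ischaemic heart disease (SMQ") and "Ischaemic central nervous system vascular conditions (SMQ").

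SAP 6.17 introduces its list with "The key safety events to be considered for H0P-MC-BP03 are listed below by domain". MACE is one of six entries under Cardiovascular there. It appears as a single word, with no definition of its own.

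Two other statements in 6.12.2 bear on the point. One is general reporting: "Treatment-emergent adverse events by preferred term will be reported". The other refers to a document that is not supplied: "The full summary of adverse events is described in the H0P-MC-CPMP SAP".

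**The concern.** The heading promises stroke without qualification. The search that should deliver it is limited, by its name, to ischaemic conditions. A programmer would reasonably treat the list as complete, because the neighbouring categories are spelled out to the same level of detail. The MACE flag would then not measure what its heading states.

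What is at stake is the accuracy of one named entry in the safety review. Protocol 2.3.1 lists cardiovascular effects as a potential risk of clinical significance, and SAP 6.17 makes MACE one of the events by which that domain is judged. In a trial of this size the MACE count will be very small, so whether a single event belongs in it should be settled before anyone knows what events occurred.

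**Working it through.** The plan gives no figure to reproduce. The check sets the label against each listed item, then looks for anything elsewhere that fills the gap.

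**Step 1: the label against the list (SAP 6.12.2)**

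| Items under MACE | Number | Would the name cover a non-fatal haemorrhagic stroke? |
|---|---|---|
| Preferred terms for death or cardiac arrest | 5 | No: none describes a non-fatal stroke |
| Ischaemic heart disease query | 1 | No: cardiac |
| Ischaemic CNS query | 1 | No: named ischaemic only |
| Total | 7 | 0 of 7 |

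A fatal haemorrhagic stroke is not clearly caught either. The five fatal or arrest items are coded terms and not outcomes, so the event would count only if it were coded to one of them.

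**Step 2: is the gap filled elsewhere?** No haemorrhagic CNS search, broader cerebrovascular search or separate stroke term appears anywhere in the protocol or SAP. Nor does any section limit the stroke component to ischaemic stroke. The redaction in 6.12.2 comes after the list of events that need narratives and does not interrupt the MACE list, so it does not explain the difference.

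**Step 3: does 6.17 recover the event within the cardiovascular domain?** The other five cardiovascular entries concern QTc prolongation, serious cardiac disorders, cardiac failure, arrhythmia and hypotension. By name, none would capture a stroke.

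**Step 4: where would the event still appear?**
- In treatment-emergent events by preferred term (6.12.2).
- In the serious adverse event summaries and listings of 6.18 and 6.19, if serious.
- In the general domain of 6.17 under "Serious adverse events related to study treatment", if judged related, or under one of the discontinuation entries, if it led to discontinuation.

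The 6.17 routes depend on a causality judgement or on discontinuation, and none of them classes the event as cardiovascular.

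**Step 5: exposure**
- Inputs: up to 200 participants randomized, 8 weeks (56 days) of treatment, assumed dropout of about 33% (Protocol 9.2, SAP 5.2). The divisor 365.25 is from SAP 6.12.1.
- No dropout: 200 × 56 / 365.25 = 30.7 patient-years, both arms together.
- All dropouts leaving at the start, as a lower bound: 200 × (1 − 0.33) = 134 participants, and 134 × 56 / 365.25 = 20.5 patient-years.

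The documents give no stroke rate. On an assumed range of 0.1 to 1 haemorrhagic strokes per 1,000 patient-years, the expected number at 30.7 patient-years is 30.7 × 0.0001 = 0.003 to 30.7 × 0.001 = 0.03.

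**The case against.** The strongest reply is that this is a labelling ambiguity whose consequence cannot be proved from what is available.

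- **Contents of the query.** The preferred terms inside the SMQ are not in the documents. A stroke coded to an unspecified term might or might not be captured. This stands: the conclusion is a reading of names and applies to an event coded as haemorrhagic.
- **The master SAP.** SAP 6.12 adds to the general safety analysis in the H0P-MC-CPMP SAP, which might define MACE more broadly or cover cerebrovascular events separately. This cannot be checked. However, 6.12.2 gives its own list for this study and does not refer MACE to the master SAP. If the master SAP is broader, the two definitions differ and still need reconciling.
- **Relevance of the risk.** Protocol 2.3.1 describes the cardiovascular risk as changes in heart rate, PR and QRS. Nothing in the documents points to a haemorrhagic cerebrovascular risk. This stands and keeps the importance low.
- **Consequence for decisions.** The available text attaches no hypothesis test or decision rule to MACE. This also stands.

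A reader might go further and infer that such a stroke would vanish from the trial's safety findings, turning one event into none. The documents do not support that: the event remains in the preferred-term and serious-event outputs, and only the MACE and cardiovascular-domain counts change. A reader might also infer that the definition carries into pooled safety reports. SAP 6.18 lists the pooled outputs, and MACE is not among them.

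**Conclusion.** The point holds as a mismatch between a label and the rule meant to deliver it. As written, the MACE list in SAP 6.12.2 leaves out a non-fatal event coded as haemorrhagic stroke, and the cardiovascular domain of 6.17 inherits the omission through the shared term. Each such event would lower those two counts by one and leave the general adverse-event reporting intact.

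The practical size is small. With about 31 patient-years at full nominal follow-up, the expected number of such events is close to zero under the assumed rates. The conclusion assumes that the SMQ covers what its name says and that the list in 6.12.2 is the working definition for this study. It is a minor correction, worth making because it is cheap and because the definition should not depend on which events turn up.

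**What to change.** Before unblinding, check how the master SAP treats MACE and stroke, then make one of two changes to SAP 6.12.2:

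- If all stroke is intended, add a haemorrhagic CNS vascular search to the MACE list.
- If only ischaemic stroke is intended, relabel the category *including MI and ischaemic stroke*.

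SAP 6.17 holds no MACE list, only the term, so it follows from 6.12.2 and needs no separate edit. The first option costs one line in the SAP and one extra search term set; the second costs a change of label. Neither affects study conduct, sample size or the efficacy analyses.
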